#### **13.2.6 Record Retention**

The investigator will maintain all study records according to ICH GCP guidelines and/or applicable local regulatory requirement(s), whichever is longest, as described in the Clinical Trial Agreement. If the investigator withdraws from the responsibility of keeping the study records, custody will be transferred to a person willing to accept the responsibility and Vertex will be notified.

#### **13.2.7 Study Termination**

At any time, Vertex may terminate this study in its entirety or may terminate this study at any particular site. In addition, for reasonable cause, either the investigators or their IRBs/IECs may terminate the study at their center.

Conditions that may lead to reasonable cause and warrant termination include, but are not limited to:

- Subject or investigator noncompliance
- Unsatisfactory subject enrollment
- Lack of adherence to protocol procedures
- Lack of evaluable and/or complete data
- Potentially unacceptable risk to study subjects
- Decision to modify drug development plan
- Decision by the FDA or other regulatory authority

Written notification that includes the reason for the clinical study termination is required.

### **13.2.8 End of Study**

The end of study is defined as the last scheduled visit (or contact) of the last subject in the study.

### **13.3 Data Quality Assurance**

Vertex or its designated representative will conduct a study site visit to verify the qualifications of each investigator, inspect clinical study site facilities, and inform the investigator of responsibilities and procedures for ensuring adequate and correct study documentation.

The investigator is required to prepare and maintain adequate and accurate case histories designed to record all observations and other data pertinent to the study for each study participant. Study data for each enrolled subject will be entered into a CRF by study site personnel using a secure, validated, web-based electronic data capture (EDC) application. Vertex will have read-only access to site-entered clinical data in the EDC application.

Instances of missing, discrepant, or uninterpretable data will be queried with the investigator for resolution. Any changes to study data will be made to the CRF and documented in an audit trail, which will be maintained within the clinical database.

### **13.4 Monitoring**

Monitoring and auditing procedures developed or approved by Vertex will be followed to comply with GCP guidelines. On-site checking of the CRFs/SAE Forms for completeness and clarity, cross-checking with source documents, and clarification of administrative matters will be performed.

The study will be monitored by Vertex or its designee. Monitoring will be done by personal visits from a representative of Vertex, or designee (study site monitor), who will review the CRFs/SAE Forms and source documents. The study site monitor will ensure that the investigation is conducted according to the protocol design and regulatory requirements.

### **13.5 Electronic Data Capture**

Vertex will provide the study sites with secure access to and training on the EDC application sufficient to permit study site personnel to enter or correct information in the CRFs on the subjects for which they are responsible.

[figure not shown]
A CRF will be completed for each enrolled study subject. It is the investigator's responsibility to ensure the accuracy, completeness, clarity, and timeliness of the data reported in the subject's CRF. Source documentation supporting the CRF data will indicate the subject's participation in the study and will document the dates and details of study procedures, AEs, other observations, and subject status.

The investigator, or designated representative, will complete the CRF as soon as possible after information is collected.

The audit trail entry will show the user's identification information and the date and time of any correction. The investigator will provide formal approval of all the information in the CRFs, including any changes made to the CRFs, to endorse the final submitted data for the subjects for whom the investigator is responsible.

Vertex will retain the CRF data and corresponding audit trails. A copy of the final archival CRF in the form of a compact disc (CD) or other electronic media will be placed in the investigator's study file.

### **13.6 Publications and Clinical Study Report**

#### **13.6.2 Clinical Study Report**

A clinical study report, written in accordance with the ICH E3 Guideline, will be submitted in accordance with local regulations.

3 INTRODUCTION

This statistical analysis plan (SAP) for the Part 1 (interim) and final analysis is based on the most recent approved clinical study protocol (CSP), electronic case report form (eCRF), and eCRF completion guidelines.

This SAP (Methods) documents the planned statistical analyses of efficacy and safety endpoints for the Part 1 analysis and the final analysis (FA), which have been pre-defined in the VX16-809-121 study protocol. It also documents analyses for [REDACTED] safety variables not specified in the protocol, which will provide supportive information for the scientific understanding of the drug entity.

The Vertex Biometrics Department will perform the statistical analysis of the efficacy and safety data; SAS (Version 9.4 or higher) will be used to generate all statistical outputs (tables, figures, listings, and datasets). The SAP will be finalized and approved prior to the Part 1 analysis data-cut and treatment unblinding for the Part 1 analysis. Any revisions to the approved SAP will be documented and approved in an amendment to the SAP prior to the clinical database lock for the final analysis. Any changes made to the SAP (Methods) after the clinical database lock has occurred will be documented in the clinical study report for this study.

4 STUDY OBJECTIVES

4.1 Primary Objective

To explore the impact of Lumacaftor/ivacaftor (LUM/IVA) on disease progression in subjects aged 2 through 5 years with CF, homozygous for *F508del*.

4.2 Secondary Objectives

To explore the relationship between lung clearance index (LCI) and imaging modalities for LUM/IVA in subjects aged 2 through 5 years with CF, homozygous for *F508del*.

5 STUDY ENDPOINTS

[figure not shown]
5.1 Efficacy Endpoints for Part 1 Analysis

5.1.1 Primary Endpoint

- Absolute change from baseline in magnetic resonance imaging (MRI) global chest score at Week 48

5.1.2 Secondary Endpoints

- Absolute change from baseline in LCI2.5 through Week 48
- Absolute change from baseline in weight-for-age z-score at Week 48
- Absolute change from baseline in stature-for-age z-score at Week 48
- Absolute change from baseline in body mass index (BMI)-for-age z-score at Week 48

[figure not shown]
6 STUDY DESIGN

6.1 Overall Design

This is a Phase 2, 2-part, randomized, double-blind, placebo-controlled, parallel-group study with a long-term open-label period in subjects 2 through 5 years of age with CF, homozygous for *F508del*. A schematic of the study design is shown in Figure 6-1.

Figure 6-1 Schematic of the Study Design

ETT: Early Termination of Treatment; IVA: ivacaftor; LUM: lumacaftor; pbo: placebo; q12h: every 12 hours.

- ^a The Safety Follow-up Visit is scheduled to occur 2 weeks (± 4 days) after the last dose. The Safety Follow-up Visit is required for 1) subjects who complete their ETT Visit <10 days after the last dose of study drug and 2) subjects who interrupt study drug treatment and complete their Week 96 Visit <10 days after the last dose of study drug; it is not required for subjects who continue onto commercially-available, physician-prescribed study drug within 2 weeks (± 4 days) of completing study drug treatment at the Week 96 or ETT Visit.
- ^b Approximately 50 subjects are planned to be randomized (2:1) to receive LUM/IVA or placebo. Subjects will receive LUM 100 mg/IVA 125 mg every 12 hours (q12h) (subjects weighing <14 kg at screening), LUM 150 mg/IVA 188 mg q12h (subjects weighing ≥ 14 kg at screening), or matching placebo (Part 1 only) during the Treatment Period.
- ^c No downward dose adjustments will be made if a subject's weight decreases. If a subject subsequently weighs ≥ 14 kg at 2 consecutive visits, the dose will be adjusted to LUM 150 mg/IVA 188 mg q12h, at the second visit where weight ≥ 14 kg. Subjects who turn 6 years of age at or after the Week 48 Visit will receive LUM 200 mg/IVA 250 mg q12h (starting at the Week 48 Visit or the next scheduled visit after turning 6 years of age), regardless of weight.
- ^d Subjects who prematurely discontinue study treatment will have an ETT Visit as soon as possible.

In Part 1, subjects will be randomized 2:1 to receive LUM/IVA or placebo. The dose regimens of LUM 100 mg/IVA 125 mg q12h (subjects weighing <14 kg at screening) and LUM 150 mg/IVA 188 mg q12h (subjects weighing ≥ 14 kg at screening) were chosen as shown in Table 6-1. If a subject weigh is ≥ 14 kg at 2 consecutive visits, the dose will be adjusted to LUM 150 mg/IVA 188 mg q12h at the second visit where weight is ≥ 14 kg. After completing Part 1, all subjects who continue to participate the open-label Part 2 will receive LUM/IVA with the planned dosages. Subjects who turn 6 years of age at or after the Week 48 Visit will receive LUM 200 mg/IVA 250 mg q12h (starting at the Week 48 Visit or the next scheduled visit after turning 6 years of age), regardless of weight.

Table 6-1 Treatment Arms and Planned Dosages

Treatment Arm	LUM Dose	IVA Dose
LUM/IVA (Weight at Screening <14 kg)	100 mg q12h	125 mg q12h
LUM/IVA (Weight at Screening ≥14 kg)	150 mg q12h	188 mg q12h
Matching Placebo	0 mg	0 mg
LUM/IVA (Age ≥6 years at or after Week 48 Visit)	200 mg q12h	250 mg q12h

LUM: lumacaftor; IVA: ivacaftor; PBO: placebo; q12h: every 12 hours

6.2 Sample Size and Power

The proposed sample size of 50 subjects (2:1 randomization: 33 LUM/IVA subjects and 17 placebo subjects) is based on the number of potential subjects expected to be available for participation. No formal sample size calculation was conducted.

6.3 Randomization

Study Part 1

The proposed sample size of 50 subjects will be randomized by 2:1 ratio to the LUM/IVA arm or placebo arm.

An interactive web or voice response system (IXRS) will be used to assign subjects to treatment or placebo. The randomization code will be produced by Vertex Biostatistics or a qualified randomization vendor.

Study Part 2

Part 2 is an open-label extension period. Randomization is not applicable.

6.4 Blinding and Unblinding

Refer to the CSP Section 10.7 for details.

6.5 Part 1 and Final Analysis

Part 1 analysis will be conducted after all subjects have completed Part 1 (i.e., up to and including the Week 48 Visit) or have prematurely discontinued. The final analysis will occur after all subjects have completed the study or have prematurely discontinued.

7 ANALYSIS SETS

The following analysis sets are defined: All Subjects Set, Full Analysis Set, [REDACTED] and Safety Set.

A summary of analysis sets is presented in Table 7-1.

Table 7-1 Summary of Analysis Sets

Analysis Set	Target Analyses	Treatment Group/Sequence
All Subject Set ^a	Individual subject listing and disposition summary for Part 1 analysis	
 LUM/IVA PBO
Full Analysis Set (FAS) ^a	Efficacy and baseline demographic for Part 1 analysis	
 LUM/IVA PBO
	By-visit efficacy summary for FA	
 LUM/IVA→LUM/IVA PBO→LUM/IVA

Safety Set ^b	Safety for Part 1 analysis	
 • LUM/IVA • PBO
	Part 2 safety analysis, individual subject listing, and disposition summary for FA	OR 
 • Overall LUM/IVA • LUM/IVA→LUM/IVA • PBO→LUM/IVA

^a Treatment label is based on the treatment the subject was randomly assigned to in the study Part 1 or the corresponding treatment sequence from Part 1 to Part 2.

^b Treatment label is based on the treatment that the subject received in the study Part 1 or its corresponding treatment sequence from Part 1 to Part 2.

[figure not shown]
FA: final analysis; IVA: ivacaftor; LUM: lumacaftor; PBO: placebo

7.1 All Subjects Set

The **All Subjects Set** will include all subjects who are randomized or receive at least 1 dose of study drug. This analysis set will be used for all individual subject data listings and disposition summary tables, unless otherwise specified.

7.2 Full Analysis Set

The **Full Analysis Set** (FAS) will include all randomized subjects who carry the intended CFTR allele mutation and receive at least 1 dose of study drug in the study Part 1. The FAS will be used to summarize subject demographics and baseline characteristics, and for all efficacy analyses, unless otherwise specified.

7.4 Safety Set

The **Safety Set** will include all subjects who receive at least 1 dose of study drug. The Safety Set will be used for all safety analyses.

8 ANALYSIS PERIOD

The analysis period used for efficacy and safety endpoints in the Part 1 Analysis or FA is described below.

8.1 Part 1 Efficacy Analysis Period

The **Part 1 Efficacy Analysis Period** will include the time from the first dose date of study drug until the last efficacy assessment in Part 1, which may be collected up to the Week 48 Visit.

[figure not shown]

8.2 Part 1 Treatment-Emergent Period

The **Part 1 Treatment-Emergent (TE) Period** will include the time from the first dose of study drug (including the matched placebo) until 14 days after the last dose of study drug of Part 1 or the completion of study participation of Part 1, whichever occurs first.

Completion of study participation of Part 1 is defined as the following:

- For subjects who complete Part 1 and enter Part 2: the day prior to the first dose of study drug of Part 2
- For subjects who prematurely discontinue study drug treatment during the Part 1 treatment period but do not withdraw consent (and assent, as applicable): the latest of the Week 48 Visit, ETT or Safety Follow-up Visit (if required)
- For subjects who withdraw consent or assent: date of withdrawal of consent or assent, whichever is earlier.

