#### Resumption of Study Drug

If a convincing alternative etiology is identified for the LFTs (ALT, AST, and total bilirubin), study drug may be resumed when levels return to baseline or are  $\leq 2 \times \text{ULN}$ , whichever is higher. Approval of the Vertex medical monitor or designee is required before resumption of study drug. Upon resumption of study drug, transaminases should be assessed weekly for 4 weeks. If a protocol-defined liver test elevation occurs within 4 weeks of rechallenge with study drug, then study drug must be discontinued, regardless of the presumed etiology.

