### 12.3.1 General Considerations

All individual subject data for all randomized subjects exposed to study drug will be presented in data listings.

**Continuous variables** will be summarized using the following descriptive summary statistics: the number of subjects (n), mean, SD, median, minimum value, and maximum value. The precision of the measurement for each continuous variable will be specified in the SAP.

**Categorical variables** will be summarized using counts and percentages. Percentages will be presented to 1 decimal place.

**Baseline value**, unless otherwise specified, will be defined as the most recent non-missing measurement (scheduled or unscheduled) collected before the initial administration of study drug. [REDACTED]

**Change (absolute change) from baseline** will be calculated as post-baseline value - baseline value. [REDACTED]

**Relative change from baseline** will be calculated as (post-baseline value - baseline value)/baseline value. [REDACTED]

**The Treatment-emergent (TE) Period** will include the time from the first dose to the Safety Follow-up Visit or 14 days after the last dose of the study drug for subjects who do not have a Safety Follow-up Visit. [REDACTED]

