8.4 Part 2 Safety Period

The **Part 2 Safety Period** will include the time from the first dose of study drug of Part 2 until 14 days after the last dose of LUM/IVA or the completion of study participation, whichever occurs first.

Completion of study participation is defined as:

- For subjects who complete the study, the latest of the ETT Visit or Safety Follow-up Visit (if required).
- For subjects who prematurely discontinue study drug treatment during the study but do not withdraw consent (and assent, as applicable): the latest of ETT or Safety Follow-up Visit (if required).
- For subjects who withdraw consent or assent: date of withdrawal of consent or assent, whichever is earlier.

The Part 2 Safety Period will be used for analysis of safety data in the FA.

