9.3.3.1 Adverse Events

For analysis purpose, AEs in FA will be classified as TEAE during the Part 2 Safety Period and Post-treatment AEs, defined as follows:

TEAE during the Part 2 safety period: any AE that worsened (either in severity or seriousness) or that was newly developed at or after the first dose date of study drug in Part 2 through the end of the Part 2 Safety Period.

Post-treatment AE: any AE that worsened (either in severity or seriousness) or that was newly developed after the Part 1 TE period if subjects who did not receive study drug in Part 2 or after the Part 2 Safety Period if subjects received study drug in Part 2.

For the overview of all TEAEs during the Part 2 Safety Period (as defined in Section 9.2.3.1), the frequency counts and percentages will be summarized.

For the summary tables of TEAEs during the Part 2 Safety Period, the frequency counts and percentages will be presented by MedDRA SOC and PT.

In addition, TEAEs during the Part 2 Safety Period and post-treatment AEs will be presented in an individual subject data listing based on the Safety Set, Part 2.

Similar as the Part 1 analysis of AESIs, the treatment-emergent elevated transaminases events and respiratory events during the Part 2 Safety Period will be summarized.

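### When the first Part 2 dose comes 16 or more days after the last Part 1 dose, adverse events and labs from off-drug day 15 until that dose fall outside both of the SAP's readable safety periods

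*SAP*

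**What the plan says.** SAP 8.2 starts the Part 1 TE Period at the first dose and runs it "until 14 days after the last dose of study drug of Part 1 or the completion of study participation of Part 1", taking the earlier. The definition of completion that applies to children going on to open-label treatment is: "For subjects who complete Part 1 and enter Part 2: the day prior to the first dose of study drug of Part 2". SAP 8.4 dates the Part 2 Safety Period "from the first dose of study drug of Part 2 until 14 days after the last dose of LUM/IVA"; an earlier end of study participation closes it sooner. It has no look-back before the first Part 2 dose.

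SAP 9.3.3.1 gives two routes to post-treatment status. For a child never dosed in Part 2, the category begins once the Part 1 TE Period has ended. For a child who was dosed in Part 2, it begins only "after the Part 2 Safety Period if subjects received study drug in Part 2".

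SAP 9.2.3 bases the Part 1 safety analyses on the Part 1 TE Period, by treatment actually received. SAP 9.2.3.2 confines the laboratory summaries, threshold counts and laboratory listing to the same period. SAP 8.4 and 9.3.3 tie the final safety analysis to the Part 2 Safety Period.

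The protocol does not split the period. Its definition in 12.3.1 "will include the time from the first dose to the Safety Follow-up Visit or 14 days after the last dose of the study drug", the latter for children without a follow-up visit. Protocol 12.3.4.6 asks for safety analyses by arm from baseline to Week 48 and from baseline to Week 96. Protocol 11.5.3 foresees interruption for raised transaminases and, under conditions, says "study drug may be resumed when levels return to baseline" or to a stated limit. It sets no maximum length for an interruption.

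**The concern.** A 14-day tail suits a child who has stopped study drug for good. SAP 8.2 also applies it to a child who is only interrupted, provided the restart happens to be the first open-label dose. The Part 1 period then closes two weeks into the interruption, and nothing opens until the restart. An interruption of similar length that ends just before Week 48 is counted in full. Nothing in the documents explains the difference.

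The one interruption-and-restart route that the protocol spells out is a liver-test elevation, and elevated transaminases are an AESI in SAP 9.2.3.1. The uncovered days can therefore hold follow-up chemistry, and any new or worsening events, in a child already under safety observation. With 33 active and 17 placebo children planned, one child is 1/33 = 3.0 or 1/17 = 5.9 percentage points of an arm's incidence. A shift of that size arises only if the child has no other counted occurrence of the same event.

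**Working it through.** The plan gives no figure of its own here. The check applies its period rules as day arithmetic.

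**Inputs**
- L = day of last Part 1 dose and P = day of first Part 2 dose. These values are assumed.
- The planned P is the Week 48 Visit (Protocol Table 3-2, footnote d), with target Day 337 (SAP Appendix A).
- End of the Part 1 TE Period (SAP 8.2, child enters Part 2) = min(L + 14, P − 1).
- Start of the Part 2 Safety Period (SAP 8.4) = P.

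**Formula**

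The uncovered days run from L + 15 to P − 1, so their number is max(0, P − L − 15).

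| L | P | P − L | TE Period ends | Uncovered days | Number |
|---|---|---|---|---|---|
| 336 | 337 | 1 | 336 | none | 0 |
| 322 | 337 | 15 | 336 | none | 0 |
| 321 | 337 | 16 | 335 | 336 | 1 |
| 300 | 337 | 37 | 314 | 315–336 | 22 |
| 280 | 337 | 57 | 294 | 295–336 | 42 |
| 300 | 360 | 60 | 314 | 315–359 | 45 |

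The gap opens only when P − L reaches 16.

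**Contrast with an interruption that ends inside Part 1.** Suppose a child takes a dose on Day 280, is off drug on Days 281–335 (55 days) and resumes on Day 336, with P = 337. Then L = 336, the period ends at min(350, 336) = 336, and all 55 off-drug days are covered. If the same child restarts one day later with the open-label dose on Day 337, L stays at 280 and 42 days are uncovered.

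**Class of a new AE on a gap day**
- Pretreatment: no, because it starts after the first dose.
- Part 1 TEAE: no, because the Part 1 TE Period has ended.
- Part 2 TEAE: no, because it precedes the first Part 2 dose.
- Post-treatment: no, because the child is dosed in Part 2 and SAP 9.3.3.1 then starts that category only after the Part 2 Safety Period.

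**Labs on a gap day.** The Appendix A chemistry window for Week 48 is Day 295 to the earlier of Day 404 (337 + 67) and the first Part 2 dose. For L = 280 and P = 337, all 42 uncovered days fall inside that window. A value there can carry the Week 48 label, yet SAP 9.2.3 and 9.2.3.2 remove it from the Part 1 summaries, threshold counts and listing. The Part 2 laboratory listing in SAP 9.3.3.2 covers Part 2 only.

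**After the fix.** With the end set to P − 1 for children who enter Part 2, the gap is (P − 1) − (P − 1) = 0 for every L and P.

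**The case against.** Several objections limit the point, and most of them stand.

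- **Hidden text.** SAP 8.3 is redacted, and Appendix C refers to a Cumulative Safety Period that the readable text never defines. If that period spans both parts, it could classify gap events. This has to be disclosed. It does not rescue the visible tables, because SAP 8.4 and 9.2.3 tie those to the Part 2 Safety Period and the Part 1 TE Period.
- **Short interruptions.** A reader might infer that any interruption across Week 48 opens a gap. It does not: up to P − L = 15 the day-before-Part-2 limb comes first and no day is lost.
- **Extent of the loss.** A reader might infer that all the safety data from such an interruption vanish. They do not. A triggering event that arises on drug, and the first 14 off-drug days, are still counted. SAP 9.2.3.1 lists all AEs and flags TEAE status for SAEs and deaths. For a placebo child, the last gap laboratory value can serve as the LUM/IVA Baseline (SAP 9.1).
- **Which arm.** The tables affected are by treatment received, not by randomised arm.
- **Extreme cases.** L = 253 with P = 404 gives 404 − 253 − 15 = 136 days. That joins a long interruption to the longest delay of Week 48. The protocol allows the delay for recovery from a pulmonary exacerbation, during which children are to stay on drug, so the figure is not representative.
- **Narrow liver route.** Under Protocol 11.5.3, resumption needs a convincing alternative cause, recovered levels and medical monitor approval. A child who stops permanently and gets no Part 2 drug is already covered by the post-treatment category.
- **The 14-day tail is the documents' own convention.** Removing it for these children counts remote off-drug days as treatment-emergent. A separate off-treatment category would also classify the events. This is a fair argument about the form of the remedy, and it is why an off-drug flag belongs in it. It does not defend leaving the days unclassified.

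**Conclusion.** The point holds in bounded form. SAP 8.2, 8.4 and 9.3.3.1, read together, leave P − L − 15 days without a class when a child's first Part 2 dose comes at least 16 days after the last Part 1 dose. New or worsening AEs on those days leave the TEAE and AESI tables. Labs leave the Part 1 summaries, threshold counts and laboratory listing. The gap comes from the SAP's split: the readable definition in Protocol 12.3.1 is continuous and would include these days.

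The day counts are illustrations, and the documents give no basis for a frequency. Few children are likely to be affected, safety is analysed descriptively only, and no efficacy endpoint is touched. The conclusion assumes that an interrupted child may enter Part 2, which no readable rule forbids, and that redacted text does not override the readable table specifications. It is worth correcting because the rule is explicit, the children concerned may be those interrupted for safety, and the repair is cheap.

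**What to change.** In SAP 8.2, state that for subjects who enter Part 2 the Part 1 TE Period runs to the day before the first Part 2 dose regardless of any interruption. Keep the 14-day limb only for subjects who permanently stop study drug in Part 1.

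Flag AEs and labs that fall more than 14 days after the last Part 1 dose as off-drug, so that readers can identify them. Align Appendix C with the periods the SAP defines, either by defining the Cumulative Safety Period or by replacing the term.

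The cost is one sentence in SAP 8.2, an edit to Appendix C, and a change to the period-flag derivation. No dosing or clinical rule changes. The downside is small: some off-drug days count as treatment-emergent, as they already do for interruptions that end within Part 1.
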